6.4.3 Exchange of single case reports

Investigators must report all SAEs and AESIs using internal eSAE reporting forms and these will be forwarded electronically to the IND office and to Genentech within the timelines described below.

MDACC will be responsible for collecting all protocol-defined Adverse Events (AEs)/Serious Adverse Events (SAEs), AEs of Special Interest (AESIs), Special Situation Reports (including pregnancy reports) and Product Complaints (with or without an AE) originating from the Study for the Product.

All protocol-defined AEs, SAEs, AESIs, Special Situation Reports (including pregnancy reports) and Product Complaints with an AE should be sent to: **E-mail: [contact]**

OR

[contact]

All Product Complaints without an AE should be sent to:

Email: [contact]

Relevant follow-up information should be submitted to Genentech Drug Safety as soon as it becomes available.

All SAEs, AESIs and pregnancy reports (including pregnancy occurring in the partner of a male study subject) where the patient has been exposed to the Genentech Product, shall be transmitted to Genentech on a MedWatch or CIOMS I or on Genentech approved SAE form within one (1) business day of the awareness date.

Additional Reporting Requirements to Genentech include the following:

- **Non-serious AEs:**

All Non-serious AEs originating from the Study will be forwarded in a quarterly report to Genentech.

Note: Investigators should also report events to their IRB as required.

- **Special Situation Reports:**

In addition to all SAEs, pregnancy reports and AESIs, the following other Special Situations Reports should be collected even in the absence of an Adverse Event and transmitted to Genentech within thirty (30) calendar days:

- Data related to the Product usage during breastfeeding
- Data related to overdose, off-label use, abuse, misuse or medication error (including potentially exposed or intercepted medication errors)
- Lack of therapeutic efficacy. In addition, reasonable attempts should be made to obtain and submit the age or age group of the patient, in order to be able to identify potential safety signals specific to a particular population.

- **Product Complaints:**

A Product Complaint is defined as any written or oral information received from a complainant that alleges deficiencies related to identity, quality, safety, strength, purity, reliability, durability, effectiveness, or performance of a product after it has been released and distributed to the commercial market or clinical trial.

All Product Complaints (with or without an AE) shall be forwarded to Genentech within one (1) business day of the awareness date.

6.4.4. IND ANNUAL REPORTS

Copies to Genentech:

All IND annual reports submitted to the FDA should be copied to Genentech. Copies of such reports should be emailed to Genentech at: Genentech Drug Safety CTV mailbox:

[contact]

MDACC will forward a copy of the Final Study Report to Genentech upon completion of the Study.

6.5 STUDY CLOSE-OUT

Any study report submitted to the FDA should be copied to Genentech. This includes all IND annual reports and the Clinical Study Report (final study report). Additionally, any literature articles that are a result of the study should be sent to Genentech. Copies of such reports should be mailed to the assigned Clinical Operations contact for the study:

Email: [contact]

[contact]

And to Genentech Drug Safety CTV oversight mail box at :
[contact]

7. DATA COLLECTION AND MANAGEMENT

7.1 DATA QUALITY ASSURANCE

The University of Texas MD Anderson Cancer Center will be responsible for data management of this study, including quality checking of the data. Data entered manually will be collected via EDC through use of eCRFs. Sites will be responsible for data entry into the EDC system. The PI will perform oversight of the data management of this study.

eCRFs and correction documentation will be maintained in the EDC system's audit trail. System backups for data stored at The University of Texas MD Anderson Cancer Center and records retention for the study data will be consistent with The University of Texas MD Anderson Cancer Center's standard procedures, which mandate that data be maintained indefinitely.

7.2 ELECTRONIC CASE REPORT FORMS

eCRFs are to be completed through use of the MD Anderson Cancer Center Prometheus EDC system.

Designated, trained site staff should complete all eCRFs. eCRFs should be reviewed and electronically signed and dated by the investigator or a designee.

SAE data will be captured via eSAE in accordance with Sponsor policy.

7.3 SOURCE DATA DOCUMENTATION

Study monitors will perform ongoing source data verification and review to confirm that critical protocol data (i.e., source data) entered into the eCRFs by authorized site personnel are accurate, complete, and verifiable from source documents.

Source documents (paper or electronic) are those in which patient data are recorded and documented for the first time. They include, but are not limited to, hospital records, clinical and office charts, laboratory notes, memoranda, patient-reported outcomes, evaluation checklists, pharmacy dispensing records, recorded data from automated instruments, copies of transcriptions that are certified after verification as being accurate and complete, microfiche, photographic negatives, microfilm or magnetic media, X-rays, patient files, and records kept at pharmacies, laboratories, and medico-technical departments involved in a clinical trial.

Before study initiation, the types of source documents that are to be generated will be clearly defined in the Trial Monitoring Plan. This includes any protocol data to be entered directly into the eCRFs (i.e., no prior written or electronic record of the data) and considered source data.

Source documents that are required to verify the validity and completeness of data entered into the eCRFs must not be obliterated or destroyed and must be retained per the policy for retention of records described in Section 7.5.

To facilitate source data verification and review, the investigators must provide the Sponsor direct access to applicable source documents and reports for trial-related monitoring, Sponsor audits, and IRB/EC review. The study site must also allow inspection by applicable health authorities.

7.4 USE OF COMPUTERIZED SYSTEMS

When clinical observations are entered directly into a study site's computerized medical record system (i.e., in lieu of original hardcopy records), the electronic record can serve as the source document if the system has been validated in accordance with health authority requirements pertaining to computerized systems used in clinical research. An acceptable computerized data collection system allows preservation of the original entry of data. If original data are modified, the system should maintain a viewable audit trail that shows the original data as well as the reason for the change, name of the person making the change, and date of the change.

7.5 RETENTION OF RECORDS

Records and documents pertaining to the conduct of this study and the distribution of IMP, including eCRFs, electronic PRO data (if applicable), Informed Consent Forms, laboratory test results, and medication inventory records, must be retained by the Principal Investigator indefinitely, in accordance with the current policy of the MD Anderson Cancer Center IND office.

Written notification should be provided to the Sponsor and Genentech Inc prior to transferring any records to another party or moving them to another location.

7.6 MONITORING

During the study, a study monitor from the University of Texas MD Anderson Cancer Center Investigational New Drug Office will have regular contacts with the investigator and team.

8. ETHICAL CONSIDERATIONS

8.1 COMPLIANCE WITH LAWS AND REGULATIONS

This study will be conducted in full conformance with the ICH E6 guideline for Good Clinical Practice and the principles of the Declaration of Helsinki, or the laws and regulations of the country in which the research is conducted, whichever affords the greater protection to the individual. The study will comply with the requirements of the ICH E2A guideline (Clinical Safety Data Management: Definitions and Standards for Expedited Reporting). Studies conducted in the United States or under a U.S. Investigational New Drug (IND) application will comply with U.S. FDA regulations and applicable local, state, and federal laws. Studies conducted in the European Union or European Economic Area will comply with the E.U. Clinical Trial Directive (2001/20/EC).

8.2 INFORMED CONSENT

The investigator or qualified designee must obtain documented consent from each potential subject or each subject's legally acceptable representative prior to participating in a clinical trial. If there are changes to the subject's status during the trial (e.g., health or age of majority

requirements), the investigator or qualified designee must ensure the appropriate consent is in place.

If applicable, the Informed Consent Form will contain separate sections for any optional procedures. The investigator or authorized designee will explain to each patient the objectives, methods, and potential risks associated with each optional procedure. Patients will be told that they are free to refuse to participate and may withdraw their consent at any time for any reason. A separate, specific signature will be required to document a patient's agreement to participate in optional procedures. Patients who decline to participate will not provide a separate signature.

The Consent Forms must be signed and dated by the patient or the patient's legally authorized representative before his or her participation in the study. The case history or clinical records for each patient shall document the informed consent process and that written informed consent was obtained prior to participation in the study.

The Consent Forms should be revised whenever there are changes to study procedures or when new information becomes available that may affect the willingness of the patient to participate. The final revised IRB/EC-approved Consent Forms must be provided to the Sponsor for health authority submission purposes.

Patients must be re-consented to the most current version of the Consent Forms (or to a significant new information/findings addendum in accordance with applicable laws and IRB/EC policy) during their participation in the study. For any updated or revised Consent Forms, the case history or clinical records for each patient shall document the informed consent process and that written informed consent was obtained using the updated/revised Consent Forms for continued participation in the study.

A copy of each signed Consent Form must be provided to the patient or the patient's legally authorized representative. All signed and dated Consent Forms must remain in each patient's study file or in the site file and must be available for verification by study monitors at any time.

Each Consent Form may also include patient authorization to allow use and disclosure of personal health information in compliance with the U.S. Health Insurance Portability and Accountability Act (HIPAA) of 1996. If the site utilizes a separate Authorization Form for patient authorization for use and disclosure of personal health information under the HIPAA regulations, the review, approval, and other processes outlined above apply except that IRB review and approval may not be required per study site policies.

8.3 INSTITUTIONAL REVIEW BOARD OR ETHICS COMMITTEE

This protocol, the Informed Consent Forms, any information to be given to the patient, and relevant supporting information must be submitted to the IRB/EC by the Principal Investigator and reviewed and approved by the IRB/EC before the study is initiated. In addition, any patient recruitment materials must be approved by the IRB/EC.

The Principal Investigator is responsible for providing written summaries of the status of the study to the IRB/EC annually or more frequently in accordance with the requirements, policies, and procedures established by the IRB/EC. Investigators are also responsible for promptly informing the IRB/EC of any protocol amendments (see Section 9.5).

In addition to the requirements for reporting all adverse events to the Sponsor, investigators must comply with requirements for reporting serious adverse events to the local health authority and IRB/EC. Investigators may receive written IND safety reports or other safety-related communications from the Sponsor. Investigators are responsible for ensuring that such reports are reviewed and processed in accordance with health authority requirements and the policies and procedures established by their IRB/EC, and archived in the site's study file.

8.4 CONFIDENTIALITY

The Sponsor maintains confidentiality standards by coding each patient enrolled in the study through assignment of a unique patient identification number. This means that patient names are not included in data sets that are transmitted to any Sponsor location.

Patient medical information obtained by this study is confidential and may be disclosed to third parties only as permitted by the Informed Consent Form (or separate authorization for use and disclosure of personal health information) signed by the patient, unless permitted or required by law.

Medical information may be given to a patient's personal physician or other appropriate medical personnel responsible for the patient's welfare, for treatment purposes.

Given the complexity and exploratory nature of exploratory biomarker analyses, data derived from these analyses will generally not be provided to study investigators or patients unless required by law. The aggregate results of any conducted research will be available in accordance with the effective Roche policy on study data publication (see Section 9.4).

Data generated by this study must be available for inspection upon request by representatives of national and local health authorities, Sponsor monitors, representatives, and collaborators, and the IRB/EC for each study site, as appropriate.

8.5 FINANCIAL DISCLOSURE

Investigators will provide the Sponsor and Genentech Inc. with sufficient, accurate financial information in accordance with local regulations to allow the Sponsor to submit complete and accurate financial certification or disclosure statements to the appropriate health authorities. Investigators are responsible for providing information on financial interests during the course of the study and for 1 year after completion of the study (i.e., LPLV).

9. STUDY DOCUMENTATION, MONITORING, AND ADMINISTRATION

9.1 STUDY DOCUMENTATION

The investigator must maintain adequate and accurate records to enable the conduct of the study to be fully documented, including, but not limited to, the protocol, protocol amendments, Informed Consent Forms, and documentation of IRB/EC and governmental approval. In addition, at the end of the study, the investigator will receive the patient data, including an audit trail containing a complete record of all changes to data.

9.2 PROTOCOL DEVIATIONS

The investigator should document and explain any protocol deviations. The investigator should promptly report any deviations that might have an impact on patient safety and data integrity to the Sponsor and Genentech Inc. and to the IRB/EC in accordance with established IRB/EC policies and procedures.

9.3 ADMINISTRATIVE STRUCTURE

This trial will be supported via the rare disease strategic alliance between The University of Texas MD Anderson Cancer Center and Genentech. The University of Texas MD Anderson Cancer Center will be the sole site, responsible for enrolling approximately 60 total patients.

The MD Anderson Cancer Center IND office will provide oversight of safety (see Section 6.0).

After written informed consent has been obtained, the study team will generate a unique study identification number for the patient.

Patient data will be recorded via an EDC system with use of eCRFs.

Central laboratories, including those at Genentech/Roche/Roche collaborators and at The University of Texas MD Anderson Cancer Center, will be used for PD-L1 expression status determination and will provide kits for pharmacogenomics, tissue, whole blood, serum, and plasma sample analyses to be conducted at central laboratories or Genentech Inc.

Treatment decisions will be made on the basis of the local reading of ECGs obtained during the study.

Imaging data will be retained at The University of Texas MD Anderson Cancer Center.

9.4 PUBLICATION OF DATA AND PROTECTION OF TRADE SECRETS

Regardless of the outcome of a trial, the Sponsor and Genentech Inc. is dedicated to openly providing information on the trial to healthcare professionals and to the public, both at scientific congresses and in peer-reviewed journals. The Sponsor will comply with all requirements for publication of study results. For more information, refer to the Roche Global Policy on Sharing of Clinical Trials Data at the following Web site:

<http://www.rochetrials.com/pdf/RocheGlobalDataSharingPolicy.pdf>

The results of this study may be published or presented at scientific congresses. For all clinical trials in patients involving an IMP for which a marketing authorization application has been filed or approved in any country, the principal investigator aims to submit a journal manuscript reporting primary clinical trial results within 6 months after the availability of the respective Clinical Study Report. In addition, for all clinical trials in patients involving an IMP for which a marketing authorization application has been filed or approved in any country, the principal investigator aims to publish results from analyses of additional endpoints and exploratory data that are clinically meaningful and statistically sound.

The investigator must agree to submit all manuscripts or abstracts to the Genentech Inc. prior to submission for publication or presentation. This allows Genentech Inc. to protect proprietary information and to provide comments based on information from other studies that may not yet be available to the investigator.

In accordance with standard editorial and ethical practice, Genentech Inc. will generally support publication of multicenter trials only in their entirety and not as individual center data. In this case, a coordinating investigator will be designated by mutual agreement.

Authorship will be determined by mutual agreement and in line with International Committee of Medical Journal Editors authorship requirements. Any formal publication of the study in which contribution of Genentech Inc. personnel exceeded that of conventional monitoring will be considered as a joint publication by the investigator and the appropriate Genentech Inc. personnel.

Any inventions and resulting patents, improvements, and/or know-how originating from the use of data from this study will become and remain the exclusive and unburdened property of the Genentech Inc., except where agreed otherwise.

9.5 PROTOCOL AMENDMENTS

The principal investigator will prepare any protocol amendments. Protocol amendments will be submitted to the IRB/EC and to regulatory authorities in accordance with local regulatory requirements.

Approval must be obtained from the IRB/EC and regulatory authorities (as locally required) before implementation of any changes, except for changes necessary to eliminate an immediate hazard to patients or changes that involve logistical or administrative aspects only (e.g., change in contact information).

Appendix 1 Study Flowchart

Day	Screening	Treatment Period						Study Completion or Early Term Visit (within 2 wks. after last dose of study drug)	Follow-Up ^k
	Day -28 to -1	C1D1 ±3day	C1D15 ±3d	C2D1 ±3d	C2D15 ±3d	C3+D1 ^l ±3d	C3+D15 ±3d		
Informed consent	X								
Demographic data	X								
Medical history	X								
Vital signs ^a	X	X	X	X	X	X	X	X	
Weight & height ^a	X	X	X	X	X	X	X	X	
Physical examination ^b	X			X		X		X	
ECOG performance status	X			X		X			
Hematology ^c	X		X	X	X	X ^p	X	X	
Chemistry ^d	X		X	X	X	X ^p	X	X	
Coagulation ^e	X			X		X ^p		X	
TSH, Free T4, Free T3	X	Every 4 cycles						X	
Viral Serology	X								
Urinalysis	X			X		X ^p		X	
Pregnancy Test ^o	X								
ECHO ^f	X	See Note						X	
Cobimetinib ^g		See Note							
Atezolizumab ^g		X	X	X	X	X	X		
Response assessment ^h	X	Scans will be done every 8 weeks ^p						X	
Complete Ophthalmologic Eval ⁱ	X			X		Every 3 cycles			
Concomitant medications ^j	X			X		X		X	
Adverse events	X			X		X		X	X

Day	Screening	Treatment Period						Study Completion or Early Term Visit (within 2 wks. after last dose of study drug)	Follow-Up ^k
		Day -28 to -1	C1D1 ±3day	C1D15 ±3d	C2D1 ±3d	C2D15 ±3d	C3+D1 ^l ±3d		
Blood Sample (Translational)		X	X					X (at progression)	
Baseline tumor tissue sample ^m	X								
Tumor biopsy (if feasible) ⁿ				X				X	

Day	Screening	Treatment Period						Study Completion or Early Term Visit (within 2 wks. after last dose of study drug)	Follow-Up ^k
	Day -28 to -1	C1D1 ±3day	C1D15 ±3d	C2D1 ±3d	C2D15 ±3d	C3+D1 ^l ±3d	C3+D15 ±3d		

Define each assessment in footnotes

^a Heart rate, systolic/diastolic blood pressure while patient in seated position, and temperature. Height to be taken at baseline (no repeat measures needed).

^b Physical examination only on day 1 of each cycle. If physical examinations are assessed within 7 days of the Cycle 1 Day 1 visit, they do not have to be repeated at Day 1.

^c Hemoglobin, hematocrit, platelet count, RBC count, WBC count, percent and absolute differential count.

^d Sodium, potassium, chloride, bicarbonate, glucose, BUN, creatinine, calcium, phosphorus, magnesium, total and direct bilirubin, total protein, albumin, ALT, AST, LDH, alkaline phosphatase, creatine phosphokinase, and uric acid.

^e Prothrombin time/International Normalized Ratio, Partial thromboplastin time, fibrinogen, D-dimer.

^f All patients will undergo evaluation of left ventricular dysfunction by ECHO at screening. Further, evaluation of LVEF by ECHO must be performed at the following timepoints: Cycle 2, Day 1 ± 1 week; Day 1 of Cycles 5, 8, and 11 (every 3 treatment cycles) ± 2 weeks; Day 1 of Cycles 15+ (every 4 treatment cycles) ± 2 weeks. If cobimetinib is permanently discontinued due to toxicity, starting 3 weeks after last dose, perform ECHO only if clinically indicated.

^g Cobimetinib is taken by mouth daily for 21 days and then 1 week off. For patient who have discontinued cobimetinib, atezolizumab can be given IV at 1680 mg once every 4 weeks.

^h Response assessment by cross-sectional imaging such as CT, MRI, or PET-CT as per standard of care for each disease. Imaging may occur up to 72 hours prior to scheduled day. Baseline assessment must occur within 28 days prior to day 1.

ⁱ Complete ophthalmologic exams will be performed at baseline (screening), C2D1 (+/- 1 week), then q 3 cycles (+/- 2 weeks). Ophthalmologic examinations will include visual acuity testing, intraocular pressure measurements by tonometry, slit-lamp ophthalmoscopy, indirect ophthalmoscopy, and spectral domain optical coherence tomography (OCT). If spectral domain OCT is not available, time-domain OCT may be performed instead. Ophthalmologic examination must be performed by a qualified ophthalmologist. If cobimetinib is permanently discontinued due to toxicity, starting 3 weeks after last dose, perform ophthalmologic exam only if clinically indicated.

^j Results of standard of care tests or examinations performed prior to obtaining informed consent and within 28 days prior to Day 1 may be used; such tests do not need to be repeated for screening

^k Required follow-up information will be collected via telephone calls and/or clinic visits every 3 months until death, withdrawal of consent, the patient is lost to follow-up, or study termination by the Sponsor, whichever occurs first.

^l Labs and restaging need not be repeated every 3rd cycle if they have been performed within 3 days as a part of restaging.

^m A pretreatment tumor biopsy is required. If pretreatment biopsy cannot be performed and archival tissue is available, archival tissue will be collected. Refer to Section 5.6.6 for tissue sample requirements.

ⁿ Screening biopsy is needed only if archival tumor tissue is unavailable or is determined to be unsuitable for required testing. On-treatment biopsy will be obtained during week 4 (within 7 days prior to Cycle 2 Day 1). Patients will undergo tumor biopsy sample collection, if deemed clinically feasible by the investigator, at the time of confirmed radiographic disease progression. Biopsies should be performed within 40 days after progression or prior to the next anti-cancer therapy, whichever is sooner. See Section 5.6.6 for tissue sample requirements.

^o Pregnancy test can be a urine/serum pregnancy test.

^p Assessments can be performed up to 7 business days prior to C3D1. Blood for translational studies can be collected within +/-1 week.

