Abbreviation: CR, complete response; IV, intravenous; mg, milligram; PD, progressive disease; PO, orally; RECIST, Response Evaluation Criteria in Solid Tumors v1.1; SD, stable disease.

*Treatment beyond initial RECIST PD can be considered in subjects experiencing clinical benefit and tolerating study therapy. In such cases confirmation of PD is recommended minimum 4 weeks after the first immune-related PD assessment. Such subjects will discontinue therapy when further progression is documented.

All patients on the study will be enrolled and receive (Figure 1): Cobimetinib 60 mg orally on Days 1–21 plus atezolizumab 840 mg IV on Day 1 and Day 15 in a 28-day cycle.

Figure 2: Treatment Schedule

The expected total length of time on study is anticipated to be approximately 15 months, with 2 weeks spent in screening, 4 weeks in washout, 12 months receiving therapy, and 2 months of follow-up prior to the final protocol visit.

Patients will undergo mandatory tumor biopsy sample collection, unless not clinically feasible as assessed and documented by the investigator, prior to cycle 2 days 1 (during week 4) and at the time of first evidence of radiographic disease progression according to RECIST v1.1 within 40 days after radiographic progression or prior to the start of new anti-cancer treatment, whichever

is sooner. These samples will be analyzed to evaluate tumor-infiltrating immune cells [ICs]). In addition, tumor tissue biomarkers related to resistance, disease progression, and clinical benefit of cobimetinib and atezolizumab may be analyzed.

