5.6.8 Follow-Up Assessments

Please see Appendix 1 for the schedule of assessments performed during the study.

- **For progression-free survival follow-up**

Patients who discontinue treatment for reasons other than disease progression (e.g., toxicity) will continue scheduled tumor assessments until disease progression, withdrawal of consent, study termination by PI, or death, whichever occurs first.

- **For survival follow-up**

Patients who discontinue study treatment for reasons other than withdrawal of consent will be followed for survival and subsequent anti-cancer therapies approximately every 3 months until death, loss to follow-up, withdrawal of consent, or study termination by PI. During this period, documentation of anti-cancer therapies should include administration start and stop dates.

Required follow-up information will be collected via telephone calls and/or clinic visits every 3 months until death, withdrawal of consent, the patient is lost to follow-up, or study termination by the Sponsor, whichever occurs first.

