- **All life-threatening or fatal events**, that are unexpected, and related to the study drug, must have a written report submitted within 24 hours (next working day) of knowledge of the event to the Safety Project Manager in the IND Office.
- Unless otherwise noted, the electronic SAE application (eSAE) will be utilized for safety reporting to the IND Office and MDACC IRB.
- Serious adverse events will be captured from the time of the first protocol-specific intervention, until 30 days after the last dose of drug, unless the participant withdraws consent. Serious adverse events must be followed until clinical recovery is complete and laboratory tests have returned to baseline, progression of the event has stabilized, or there has been acceptable resolution of the event.
- Additionally, any serious adverse events that occur after the 30 day time period that are related to the study treatment must be reported to the IND Office. This may include the development of a secondary malignancy.

Reporting to FDA:

- Serious adverse events will be forwarded to FDA by the IND Sponsor (Safety Project Manager IND Office) according to 21 CFR 312.32.

It is the responsibility of the PI and the research team to ensure serious adverse events are reported according to the Code of Federal Regulations, Good Clinical Practices, the protocol guidelines, the sponsor's guidelines, and Institutional Review Board policy.

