6.3 METHODS AND TIMING FOR ASSESSING AND RECORDING SAFETY VARIABLES

The investigator is responsible for ensuring that all AEs and SAEs that are observed and reported during the study are collected, recorded on the Adverse Event eCRF, and reported to the FDA, appropriate IRB(s), and Genentech, Inc. in accordance with CFR 312.32 (IND Safety Reports).

Investigators will seek information on adverse events at each patient contact. All adverse events (all grades and attributions), whether reported by the patient or noted by study personnel, will be recorded in the patient's medical record and on the Adverse Event eCRF.

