6.3.1 Adverse Event Reporting Period

All AEs and SAEs where the patient has been exposed to Genentech product must be reported. Reporting period begins after informed consent is obtained and ends 30 days following the last administration of study treatment or study discontinuation/termination, whichever is earlier. After this period, investigators should only report SAEs that are attributed to prior study treatment.

During screening AEs are not recorded unless they are SAEs which are related to protocol-mandated procedures. ALL AEs (including SAEs) must be recorded from the time of first atezolizumab and cobimetinib administration and end 30 days following the last administration of atezolizumab and/or cobimetinib or study discontinuation/termination, whichever is earlier. After this period, investigators should only report SAEs that are attributed to prior study treatment.

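### Adverse events are recorded to 30 days after the last dose, but Appendix 1 schedules no contact near Day 30, so at least the last 16 days have no planned safety review

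*Combined protocol and SAP*

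**What the plan says.** **Recording window.** Section 6.3.1 says that the adverse event reporting period "ends 30 days following the last administration of study treatment or study discontinuation/termination, whichever is earlier". Section 6.2.3 captures serious events "until 30 days after the last dose of drug", unless consent is withdrawn; it does not add the earlier end at study discontinuation or termination.

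**Scheduled contacts after treatment.** Appendix 1 has two columns after the treatment period. The first is headed "Study Completion or Early Term Visit (within 2 wks. after last dose of study drug". The second is Follow-Up, and its footnote k reads: "Required follow-up information will be collected via telephone calls and/or clinic visits every 3 months until death". Section 5.6.8 describes the same contacts, with patients "followed for survival and subsequent anti-cancer therapies approximately every 3 months until death". Neither place says whether the three months run from the last dose or from the completion visit. Section 4.1 gives a different expectation, "2 months of follow-up prior to the final protocol visit", which also sets nothing at Day 30.

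**How events are elicited.** The adverse events row of Appendix 1 is marked at both the completion visit and Follow-Up. Section 6.3 adds: "Investigators will seek information on adverse events at each patient contact".

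**The concern.** The protocol defines a 30-day window but plans its last close review for no later than Day 14. From then until the first follow-up contact, nothing in the schedule prompts the study team to ask about new events.

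The safety profile is a stated objective (Section 3.2). It is reported as toxicity frequency tables by tumor group (Section 5.10.3), with 20 patients planned in each. Toxicity after stopping treatment is plausible by the protocol's own account: Section 5.5.3 notes that stopping atezolizumab may not bring immediate relief of immune-mediated toxicity, and Section 5.4.2 bars live vaccines for 90 days after the last infusion.

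An event that starts late in the window may be dated and graded from memory weeks later. It may also go unrecorded if the patient dies later or is lost before the next contact. Serious events and events of special interest have faster reporting, but the clock to the drug supplier in Section 6.4.3 runs "within one (1) business day of the awareness date". An event nobody has asked about, and that the patient has not volunteered, does not start that clock.

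**Working it through.** The plan states no figure for this gap, so there is none to reproduce. The check is day arithmetic, with Day 0 as the last dose.

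**Inputs from the documents**
- End of recording window: Day 30 (Sections 6.2.3 and 6.3.1).
- Latest day for the completion visit: Day 14 (Appendix 1).
- Follow-up interval: 3 months (Section 5.6.8; Appendix 1, footnote k).
- Expected follow-up before the final visit: 2 months (Section 4.1).
- Scan interval off treatment: 8 weeks = 56 days, for patients who stop without progression or loss of clinical benefit (Section 5.6.5).

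**Step 1: days of the window left after the completion visit.** Gap = 30 − visit day.

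| Visit day | Days left | Share of 30 |
|---|---|---|
| 14 | 30 − 14 = 16 | 53% |
| 7 | 30 − 7 = 23 | 77% |
| 1 | 30 − 1 = 29 | 97% |

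The 16-day minimum follows directly from the documents for any visit held within its limit. A visit held late, outside the limit, would leave fewer days.

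**Step 2: possible recall delay for an event starting on Days 15–30.** Delay = day of next contact − day of onset. This step rests on assumptions, because the start of follow-up is not stated. I take 2 months as 61 days and 3 months as 91 days.
- Contact 2 months after the last dose (Day 61): 61 − 30 = 31 to 61 − 15 = 46 days.
- Contact 3 months after the last dose (Day 91): 91 − 30 = 61 to 91 − 15 = 76 days.
- Contact 3 months after a Day 14 visit (Day 14 + 91 = 105): 105 − 30 = 75 to 105 − 15 = 90 days.

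The range over these assumptions is 31 to 90 days. It applies only to patients still on study with no other contact in between.

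**Step 3: incidental contacts.** If scan timing is random relative to the last dose (an assumption), an 8-weekly scan falls in a 16-day gap with probability 16/56 = 29%. About 71% of patients who stop without progression would then have no scan in the gap. For patients who progress, a biopsy where feasible may fall within 40 days after progression (Appendix 1, footnote n), but that is counted from progression and not from the last dose. The unscheduled visit in Section 5.6.7 requires that a problem be known. None of these contacts is timed to close the safety window.

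**Step 4: with a contact on Day 30 to Day 37.** The part of the window with no scheduled review falls to 0 days. The delay for an event starting on Days 15–30 becomes 30 − 30 = 0 to 30 − 15 = 15 days for a contact on Day 30, and 37 − 30 = 7 to 37 − 15 = 22 days for one on Day 37.

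**The case against.** The best defence is that nothing here contradicts itself. A recording window defines what is reportable; it does not promise a visit. Late capture is provided for in several ways:
- Adverse events are marked at Follow-Up and sought at each contact.
- Unscheduled visits are foreseen for any safety issue.
- Patients are told to report delayed infusion symptoms (Section 5.3.1) and diarrhea (Appendix 6).
- Serious events are followed until they resolve or stabilise, and related ones remain reportable after Day 30 (Section 6.2.3).
- Deaths in the reporting period are reported whatever their cause (Section 6.4.2.2).
- Each report to the IND Office updates patients already reported (Section 5.10.3).

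Most of this stands. A reader might infer that events after the completion visit are not collected at all; the documents do not support that. What remains is the non-serious event that the patient does not volunteer and that no incidental contact brings up.

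A second defence is that the completion visit itself ends the window, because Section 6.3.1 closes recording early at study discontinuation or termination. This reading is unlikely. Section 5.9 uses study discontinuation for the whole trial, adverse events are marked again at Follow-Up, patients in survival follow-up remain on study, and Section 6.2.3 puts no such limit on serious events. That the reading is possible at all is a reason to settle it in the text.

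**Conclusion.** The point holds as a gap in scheduling. At least the last 16 of the 30 days have no planned safety review if the completion visit is held on time, and more if it is held early. The consequence is delayed or recalled capture of mainly non-serious, unvolunteered events in tables that carry no formal test.

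Only the 16-day minimum comes from the documents. The 31 to 90 day recall range rests on assumed start points, and the 29% scan figure on random timing. The number of events missed or misgraded cannot be estimated.

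A reader might also infer that the trial's decisions are at risk. They are not: the primary endpoint is objective response, and the Section 5.10.5 rule counts toxicity during treatment. This is a cheap improvement worth making, not a flaw in the trial's inference.

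**What to change.** Add one safety contact, by telephone or in clinic, at Day 30 (+7 days) after the last dose of the last study drug received, that is, once both atezolizumab and cobimetinib have been permanently stopped. The anchor matters: Sections 5.3 and 5.5.1 let one drug continue after the other stops, so counting from the first drug stopped could place a closing call while the patient is still on treatment.

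The contact should review adverse events, serious adverse events and events of special interest with onset up to Day 30. Enter it as a column in Appendix 1 between the completion visit and Follow-Up, cite it in Section 6.3.1, and state there that the completion visit does not itself end the recording window.

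The cost is at most about 60 short calls (3 groups × 20 patients, one call each for those still on study), one flowchart column and a short addition to Section 6.3.1. No new procedure or sample is needed.
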